7.1.5.2 Treatment Cycles

Visit requirements are outlined in Section 6.0 (Trial Flow Chart). Specific procedure-related details are provided above in Section 7.1 (Trial Procedures).

7.1.5.2.1 Second Course Phase (Retreatment Period)

Subjects who stop pembrolizumab with SD or better may be eligible for up to 17 additional trial treatments (approximately 1 year) if they progress after stopping study treatment. This retreatment is termed the Second Course Phase of this study and is only available if the study remains open and the subject meets the following conditions:

- **Either**
 - Stopped initial treatment with pembrolizumab after attaining an investigator-determined confirmed CR according to RECIST 1.1, and
 - Was treated for at least 24 weeks with pembrolizumab before discontinuing therapy
 - Received at least two treatments with pembrolizumab beyond the date when the initial CR was declared

OR

- Had SD, PR or CR and stopped pembrolizumab treatment after 35 trial treatments (approximately 2 years) for reasons other than disease progression or intolerability

AND

- Experienced an investigator-determined confirmed radiographic disease progression or clinical progression after stopping their initial treatment with pembrolizumab.

Subjects being considered for second course retreatment after experiencing clinical progression may only be enrolled in second course after consultation with the Sponsor.

- Did not receive any anti-cancer treatment since the last dose of pembrolizumab
- Has a performance status of 0 or 1 on the ECOG Performance Scale
- Demonstrates adequate organ function as detailed in Section 5.1.2
- Female subject of childbearing potential must have a negative serum or urine pregnancy test within 72 hours prior to receiving retreatment with study medication. If the urine test is positive or cannot be confirmed as negative, a serum pregnancy test will be required.
- Female subject of childbearing potential (Section 5.7.1) should be willing to use an adequate method of contraception as outlined in Section 5.7.1- Contraception, for the retreatment period of the study through 120 days after the last dose of study medication.

Note: Abstinence is acceptable if this is the usual lifestyle and preferred contraception for the subject.

- Does not have a history or current evidence of any condition, therapy, or laboratory abnormality that might interfere with the subject's participation for the full duration of the trial or is not in the best interest of the subject to participate, in the opinion of the treating investigator.

Subjects who restart treatment will be retreated at the same dose and dose interval as when they last received pembrolizumab. Pembrolizumab will be administered for up to an additional 17 trial treatments (approximately 1 year).

Visit requirements are outlined in Section 6.0 (Trial Flow Chart).

7.1.5.3 Post-Treatment

7.1.5.3.1 Discontinuation Visit

The Discontinuation Visit should occur at the time study treatment is discontinued for any reason. If the Discontinuation Visit occurs 30 days from the last dose of study treatment, at the time of the mandatory Safety Follow-up Visit, procedures do not need to be repeated. Visit requirements are outlined in Section 6.0 (Trial Flow Chart). Specific procedure-related details are provided above in Section 7.1 (Trial Procedures). Additional details regarding subject withdrawal and discontinuation are presented in Section 5.8.

7.1.5.3.2 Safety Follow-up Visit

The mandatory Safety Follow-up Visit should be conducted approximately 30 days after the last dose of trial treatment or before the initiation of a new anti-cancer treatment, whichever comes first. All AEs that occur prior to the Safety Follow-up Visit should be recorded. Subjects with an AE of Grade >1 will be followed until the resolution of the AE to Grade 0 to 1 or until the beginning of a new anti-cancer therapy, whichever occurs first. Serious adverse events that occur within 90 days of the end of treatment or before initiation of a new

anti-cancer treatment should also be followed and recorded regardless of causality. Beyond 90 days, only SAE and ECIs that are considered related to trial treatment should be reported.

Subjects who are eligible for retreatment with pembrolizumab (as described in Section 7.1.5.2.1) may have up to 2 safety follow-up visits, 1 after the Treatment Period and 1 after the Second Course Phase.

7.1.5.3.3 Follow-up Visits

Subjects who discontinue trial treatment for a reason other than disease progression will move into the Follow-up Phase and should be assessed per study schedule to monitor disease status. The Sponsor may request survival status to be assessed at additional time points during the course of the study (not to exceed approximately 12 weeks). Every effort should be made to collect information regarding disease status until the start of new anti-cancer therapy, disease progression, death, end of trial (or if the subject begins retreatment with pembrolizumab as detailed in Section 7.1). Information regarding post-trial anti-cancer treatment will be collected if new treatment is initiated.

Subjects who are eligible to receive retreatment with pembrolizumab according to the criteria in Section 5.2.3 will move from the Follow-up Phase to the Second Course Phase when they experience disease progression. Details are provided in the Trial Flow Chart (Section 6) for retreatment with pembrolizumab.

7.1.5.3.4 Survival Follow-up

Subjects who experience confirmed disease progression or start a new anti-cancer therapy, will move into the Survival Follow-up Phase and should be contacted by telephone approximately Q12W to assess for survival status until death, withdrawal of consent, or the end of the trial, whichever occurs first.

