5.2.1.2 Dose Modification and Toxicity Management Guidelines for Pembrolizumab

Adverse events associated with pembrolizumab exposure may represent an immunologic etiology. These irAEs may occur shortly after the first dose or several months after the last dose of pembrolizumab treatment and may affect more than 1 body system simultaneously. Therefore, early recognition and initiation of treatment is critical to reduce complications. Based on existing clinical trial data, most irAEs were reversible and could be managed with interruptions of pembrolizumab, administration of corticosteroids, and/or other supportive care. For suspected irAEs, ensure adequate evaluation to confirm etiology or exclude other causes. Additional procedures or tests such as bronchoscopy, endoscopy, skin biopsy may be included as part of the evaluation. Based on the severity of irAEs, withhold or permanently discontinue pembrolizumab and administer corticosteroids. Dose modification and toxicity management guidelines for irAEs associated with pembrolizumab are provided in [Table 3](#).

Table 3 Dose Modification and Toxicity Management Guidelines for Immune-related AEs Associated with Pembrolizumab

General instructions:				

 Corticosteroid taper should be initiated upon AE improving to Grade 1 or less and continue to taper over at least 4 weeks. For situations where pembrolizumab has been withheld, pembrolizumab can be resumed after AE has been reduced to Grade 1 or 0 and corticosteroid has been tapered. Pembrolizumab should be permanently discontinued if AE does not resolve within 12 weeks of last dose or corticosteroids cannot be reduced to ≤ 10 mg prednisone or equivalent per day within 12 weeks. For severe and life-threatening irAEs, IV corticosteroid should be initiated first followed by oral steroid. Other immunosuppressive treatment should be initiated if irAEs cannot be controlled by corticosteroids. 				
irAEs	Toxicity grade or conditions (NCI CTCAE v4.0)	Action taken to pembrolizumab	irAE management with corticosteroid and/or other therapies	Monitor and follow-up

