7.1.1.6 Subsequent Anti-Cancer therapy Status

All new anti-cancer therapy initiated after the study start must be recorded in the subsequent anti-cancer therapy eCRF page. If a subject initiates another anti-cancer therapy while receiving pembrolizumab, pembrolizumab must be discontinued and subject will move into Survival Follow-up Phase; if a subject initiates a new anti-cancer therapy within 30 days after the last dose of the trial treatment, the 30 day Safety Follow-up visit must occur before the first dose of the new therapy.

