All adverse events that occur after the consent form is signed but before treatment allocation/randomization must be reported by the investigator if they cause the subject to be excluded from the trial, or are the result of a protocol-specified intervention, including but not limited to washout or discontinuation of usual therapy, diet, placebo treatment or a procedure. From the time of treatment allocation/randomization through 30 days following cessation of treatment, all adverse events must be reported by the investigator. Such events will be recorded at each examination on the Adverse Event case report forms/worksheets. The reporting timeframe for adverse events meeting any serious criteria is described in section 7.2.3.1. The investigator will make every attempt to follow all subjects with non-serious adverse events for outcome.

Electronic reporting procedures can be found in the EDC data entry guidelines. Paper reporting procedures can be found in the Investigator Trial File Binder (or equivalent).

7.2.1 Definition of an Overdose for This Protocol and Reporting of Overdose to the Sponsor

For purposes of this trial, an overdose will be defined as any dose exceeding the prescribed dose of 1000 mg or greater (≥ 5 times the indicated dose). No specific information is available on the treatment of overdose of pembrolizumab. In the event of overdose, pembrolizumab should be discontinued and the subject should be observed closely for signs of toxicity. Appropriate supportive treatment should be provided if clinically indicated.

If an adverse event(s) is associated with ("results from") the overdose of Sponsor's product or vaccine, the adverse event(s) is reported as a serious adverse event, even if no other seriousness criteria are met.

If a dose of Sponsor's product or vaccine meeting the protocol definition of overdose is taken without any associated clinical symptoms or abnormal laboratory results, the overdose is reported as a non-serious Event of Clinical Interest (ECI), using the terminology "accidental or intentional overdose without adverse effect."

All reports of overdose with and without an adverse event must be reported by the investigator within 24 hours to the Sponsor either by electronic media or paper. Electronic

reporting procedures can be found in the EDC data entry guidelines. Paper reporting procedures can be found in the Investigator Trial File Binder (or equivalent).

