7.2.3 Immediate Reporting of Adverse Events to the Sponsor

7.2.3.1 Serious Adverse Events

A serious adverse event is any adverse event occurring at any dose or during any use of Sponsor's product that:

- Results in death;
- Is life threatening;
- Results in persistent or significant disability/incapacity;
- Results in or prolongs an existing inpatient hospitalization;
- Is a congenital anomaly/birth defect;
- Is an other important medical event.

Note: In addition to the above criteria, adverse events meeting either of the below criteria, although not serious per ICH definition, are reportable to the Sponsor in the same timeframe as SAEs to meet certain local requirements. Therefore, these events are considered serious by the Sponsor for collection purposes.

- Is a new cancer (that is not a condition of the study);
- Is associated with an overdose.

Refer to [Table 7](#) for additional details regarding each of the above criteria.

For the time period beginning when the consent form is signed until treatment allocation/randomization, any serious adverse event, or follow up to a serious adverse event, including death due to any cause other than progression of the cancer under study (reference Section 7.2.3.3 for additional details), that occurs to any subject must be reported within 24 hours to the Sponsor if it causes the subject to be excluded from the trial, or is the result of a protocol-specified intervention, including but not limited to washout or discontinuation of usual therapy, diet, placebo treatment or a procedure.

For the time period beginning at treatment allocation/randomization through 90 days following cessation of treatment, or 30 days following cessation of treatment if the subject initiates new anticancer therapy, whichever is earlier, any serious adverse event, or follow up to a serious adverse event, including death due to any cause other than progression of the cancer under study (reference Section 7.2.3.3 for additional details), whether or not related to the Sponsor's product, must be reported within 24 hours to the Sponsor either by electronic media or paper. Electronic reporting procedures can be found in the EDC data entry guidelines. Paper reporting procedures can be found in the Investigator Trial File Binder (or equivalent).

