Additionally, any serious adverse event, considered by an investigator who is a qualified physician to be related to the Sponsor's product that is brought to the attention of the investigator at any time following consent through the end of the safety follow-up period specified in the paragraph above, or at any time outside of the time period specified in the previous paragraph also must be reported immediately to the Sponsor.

All subjects with serious adverse events must be followed up for outcome.

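### SAEs are required to Day 90, but subjects who stop for progression and start no new therapy have no scheduled adverse-event review after the Day 30 visit

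*Combined protocol and SAP*

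**What the plan says.** **Obligation.** Protocol section 7.2.3.1 requires SAEs, related or not, to be reported "through 90 days following cessation of treatment, or 30 days following cessation of treatment if the subject initiates new anticancer therapy, whichever is earlier". The reason for stopping plays no part. For all adverse events, section 7.2 runs from allocation "through 30 days following cessation of treatment, all adverse events must be reported by the investigator", with no exception for new therapy.

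**Schedule.** The adverse-event review row of flow chart 6.1 has 12 marks: screening, eight cycle columns, discontinuation, safety follow-up and follow-up visits. Flow chart 6.2 has 11 (the same without screening). In both, the Survival Follow-Up cell is empty.

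**Who goes where.** Section 7.1.5.3.3: "Subjects who discontinue trial treatment for a reason other than disease progression will move into the Follow-up Phase". Under section 7.1.5.3.4, subjects with confirmed progression or new therapy enter Survival Follow-up and "should be contacted by telephone approximately Q12W to assess for survival status". No date is given from which the first call is counted.

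**Early switchers.** If new therapy starts within 30 days of the last dose, section 7.1.1.6 says "the 30 day Safety Follow-up visit must occur before the first dose of the new therapy".

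**Late events.** Section 5.2.1.2 says of immune-related events: "These irAEs may occur shortly after the first dose or several months after the last dose of pembrolizumab treatment".

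**The concern.** A reporting window is only as good as the contacts at which someone asks. The protocol asks for SAEs over 90 days in all subjects who have not started other therapy, but it schedules the question after Day 30 only for those who stopped without progression. Detection in Days 31 to 90 is then planned in one group and left to unscheduled reporting in the other.

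This matters for two reasons. First, the drug class is one for which the protocol itself expects late immune-related toxicity, so serious late events are part of what the safety objective should describe. Second, ascertainment that depends on disease outcome makes the SAE and Grade 4/5 summaries harder to interpret: a low count after Day 30 in progressors could mean few events or few enquiries.

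**Working it through.** The plan gives no figure to reproduce here; the check compares the obligation with the schedule.

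**1. Contacts that serve the Day 31 to 90 window (7.2.3.1 against 6.1, 6.2, 7.1.5.3.2 to 7.1.5.3.4)**

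| Reason for stopping | New therapy by Day 90 | SAE window under 7.2.3.1 | Scheduled adverse-event review after the Day 30 visit |
|---|---|---|---|
| Not progression | No | 90 days | Yes, Follow-up Visits |
| Progression | No | 90 days | None |
| Progression | Yes | 30 days | None, and none needed under this wording |

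The mismatch is the second row. It covers 90 − 30 = 60 of 90 days (67%). That is a share of days, not of events.

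**2. Timing of the first survival call.** Twelve weeks is 84 days, and the flow-chart window is ±7 days.
- Counted from last dose: Day 84 (77 to 91).
- Counted from a point one three-week cycle later: 21 + 84 = Day 105 (98 to 112).
- Counted from the Day 30 visit: 30 + 84 = Day 114 (107 to 121).

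So the call may fall inside or well outside the window, and in no case is an SAE question attached to it.

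**3. How many subjects.** Exposed = N × p × (1 − s), with N = 325 (section 1.0), p the share stopping for progression and s the share of those starting new therapy by Day 90. The documents give neither p nor s. Two indirect guides are the expected response rate of about 25% (section 8.9) and the earlier ovarian cohort, where 4 of 26 were still on treatment without progression, leaving 22/26 = 84.6% (section 4.1.2; reasons for stopping not given). I take p = 75% and 85% as assumptions.

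| p | s = 0% | s = 40% | s = 80% |
|---|---|---|---|
| 75% | 244 (75%) | 146 (45%) | 49 (15%) |
| 85% | 276 (85%) | 166 (51%) | 55 (17%) |

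For example, 325 × 0.75 × 0.60 = 146 and 325 × 0.75 × 0.20 = 49.

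**4. When is the exposed group a majority?** It needs p(1 − s) > 0.5, that is s < 1 − 0.5/p: below 33% for p = 75% and below 41% for p = 85%. Over p = 65% to 95% the threshold runs from 23% to 47%.

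**5. Subjects who switch therapy.** Take a switch on Day 10. The Safety Follow-up Visit must come before Day 10, while section 7.2 wants all adverse events to Day 30, so about 30 − 10 = 20 days have no scheduled review. Section 7.1.5.3.2, however, asks for adverse events only up to that visit, and for SAEs within 90 days or before new therapy; an early visit satisfies that wording. Now take a switch on Day 70. Section 7.1.5.3.2 asks for SAEs through Day 69, so Days 31 to 69 have no scheduled review, while section 7.2.3.1 shortens the window to 30 days. The counts in step 3 use 7.2.3.1; under 7.1.5.3.2, subjects switching between Day 31 and Day 90 would be added for part of the window.

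**The case against.** The strongest reply is that the duty to report does not depend on a visit. All SAEs to Day 90 are reportable within 24 hours whatever the reason for stopping. For related SAEs that reach the investigator, section 7.2.3.1 extends the duty: "or at any time outside of the time period specified in the previous paragraph also must be reported immediately to the Sponsor". Section 7.1.5.3.2 has open events above Grade 1 followed to Grade 0 to 1 or new therapy. Survival calls will find deaths. Flow chart 6.1 marks a medication review at Survival Follow-Up, and section 5.5.1 limits medications recorded after Day 30 to those for SAEs and events of clinical interest, so that call is not purely a survival check. Progressors also have the Discontinuation Visit and the mandatory Safety Follow-up Visit.

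Much of this stands, and it is why under-counting is a risk and not a finding. It does not close the gap. A duty to report applies once the site knows of the event. Follow-up of open events does not find new ones. The medication review in 6.1 presupposes that the SAE has been identified, and flow chart 6.2 does not mark it in the survival column. A death found by telephone leaves non-fatal SAEs unasked. None of these provisions schedules an enquiry about new SAEs between Day 31 and Day 90.

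**Conclusion.** The point holds in a limited form. For subjects who stop for progression and start no new therapy, SAE capture in Days 31 to 90 rests on unscheduled reporting, whereas subjects who stop for other reasons are asked. The size cannot be derived from the documents; 49 to 146 of 325 is an illustration that assumes 75% stop for progression and 80% to 40% of them switch by Day 90. Safety data capture alone is affected; the response-rate analyses are not.

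A reader might infer more, but the documents do not support it:

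- **That most of the population is affected.** Under section 7.2.3.1, progressors who switch have a 30-day window, and a majority arises only if switching is below the thresholds shown in step 4.
- **That late immune-related events in general are lost through this gap.** Section 7.2 ends non-serious adverse-event reporting at Day 30 for everyone. Only SAEs, including serious immune-related ones, are at issue.
- **That a PD-L1_H versus all-comer safety comparison is distorted.** None is planned: protocol section 8.6.2 summarises the groups separately, and section 3.6.2 of the supplemental SAP names no comparison.
- **That the planned incidences are biased downward.** Neither of those sections states an analysis window, and no missed event is shown.
- **That early switchers certainly have a gap.** They do under sections 7.2 and 7.2.3.1, but not under 7.1.5.3.2. That is a conflict of wording to be reconciled.

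**What to change.** 1. In 6.1, 6.2 and 7.1.5.3.4, anchor the first survival call to the last dose, place it at about Day 90, and mark an SAE review (including serious immune-related events) for subjects who have not started new therapy. Let the call window run later, not earlier: with ±7 days a call on Day 83 would leave a week unasked.
2. Reconcile section 7.1.5.3.2 with 7.2 and 7.2.3.1 on the reporting window when new therapy brings the safety visit forward. If the 30-day window stands, add a short adverse-event enquiry at Day 30 for those subjects.
3. In protocol section 8.6.2 and supplemental SAP section 3.6.2, state the window of each safety summary. Label non-serious adverse events and Grade 2 or higher immune-related incidence as through 30 days after last dose. Collection of non-serious immune-related events need not be extended.

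The cost is a flow-chart and wording amendment, one planned call re-timed with a few questions added, some extra data entry, and one short extra call for early switchers. Events found in that extra call may be confounded by the new therapy. No treatment, sample size or efficacy analysis changes.

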7.1.5.4 Survival Status

To ensure current and complete survival data is available at the time of database locks, updated survival status may be requested during the course of the study by the Sponsor. For example, updated survival status may be requested prior to, but not limited to, an external Data Monitoring Committee review, interim and/or final analysis. Upon Sponsor notification, all participants who do not/will not have a scheduled study visit or study contact during the Sponsor-defined time period will be contacted for their survival status (excluding participants that have a previously recorded death event in the collection tool).

7.2 Assessing and Recording Adverse Events

An adverse event is defined as any untoward medical occurrence in a patient or clinical investigation subject administered a pharmaceutical product and which does not necessarily have to have a causal relationship with this treatment. An adverse event can therefore be any unfavourable and unintended sign (including an abnormal laboratory finding, for example), symptom, or disease temporally associated with the use of a medicinal product or protocol-specified procedure, whether or not considered related to the medicinal product or protocol-specified procedure. Any worsening (i.e., any clinically significant adverse change in

frequency and/or intensity) of a preexisting condition that is temporally associated with the use of the Sponsor's product, is also an adverse event.

Changes resulting from normal growth and development that do not vary significantly in frequency or severity from expected levels are not to be considered adverse events. Examples of this may include, but are not limited to, teething, typical crying in infants and children and onset of menses or menopause occurring at a physiologically appropriate time.

Sponsor's product includes any pharmaceutical product, biological product, device, diagnostic agent or protocol-specified procedure, whether investigational (including placebo or active comparator medication) or marketed, manufactured by, licensed by, provided by or distributed by the Sponsor for human use.

Adverse events may occur during clinical trials, or as prescribed in clinical practice, from overdose (whether accidental or intentional), from abuse and from withdrawal.

Progression of the cancer under study is not considered an adverse event.

All adverse events that occur after the consent form is signed but before treatment allocation/randomization must be reported by the investigator if they cause the subject to be excluded from the trial, or are the result of a protocol-specified intervention, including but not limited to washout or discontinuation of usual therapy, diet, placebo treatment or a procedure. From the time of treatment allocation/randomization through 30 days following cessation of treatment, all adverse events must be reported by the investigator. Such events will be recorded at each examination on the Adverse Event case report forms/worksheets. The reporting timeframe for adverse events meeting any serious criteria is described in section 7.2.3.1. The investigator will make every attempt to follow all subjects with non-serious adverse events for outcome.

Electronic reporting procedures can be found in the EDC data entry guidelines. Paper reporting procedures can be found in the Investigator Trial File Binder (or equivalent).

7.2.1 Definition of an Overdose for This Protocol and Reporting of Overdose to the Sponsor

For purposes of this trial, an overdose will be defined as any dose exceeding the prescribed dose of 1000 mg or greater (≥ 5 times the indicated dose). No specific information is available on the treatment of overdose of pembrolizumab. In the event of overdose, pembrolizumab should be discontinued and the subject should be observed closely for signs of toxicity. Appropriate supportive treatment should be provided if clinically indicated.

If an adverse event(s) is associated with ("results from") the overdose of Sponsor's product or vaccine, the adverse event(s) is reported as a serious adverse event, even if no other seriousness criteria are met.

If a dose of Sponsor's product or vaccine meeting the protocol definition of overdose is taken without any associated clinical symptoms or abnormal laboratory results, the overdose is reported as a non-serious Event of Clinical Interest (ECI), using the terminology "accidental or intentional overdose without adverse effect."

All reports of overdose with and without an adverse event must be reported by the investigator within 24 hours to the Sponsor either by electronic media or paper. Electronic

reporting procedures can be found in the EDC data entry guidelines. Paper reporting procedures can be found in the Investigator Trial File Binder (or equivalent).

